### **RANDOMIZATION VISIT AND TREATMENT PERIOD:**

At the Randomization Visit, the 2-week sleep diary and laboratory results will be reviewed for definitive eligibility before the participant is randomized to treatment. Baseline subjective sleep measures will be determined from this 2-week period. Baseline questionnaires will be determined at the Randomization Visit; these questionnaires will be determined again at both the 6-week and 12-week visits. HbA1c and C-Reactive Protein tests will only be performed at the Randomization Visit if more than 4 weeks have elapsed between this visit and the Screening Visit. Baseline pre-treatment symptom measures will be determined at the Randomization Visit. Eligible participants will be randomized in a 2:1 ratio to 6 weeks of placebo or suvorexant. At their 6-week visit, placebo non-responders will be re-randomized to either suvorexant or placebo in a 1:1 ratio. The placebo non-responders will be determined by the unblinded research coordinator, who will review the 2 weeks of sleep diaries completed before the 6-week visit.

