### **Inclusion Criteria:**

- 1) Men or women of any ethnic origin
- 2) Written informed consent is obtained
- 3) Speaks and writes in English
- 4) A willingness and ability to comply with study procedures.
- 5) Age 25–75 years
- 6) Diagnosis of Type 2 diabetes with suboptimally controlled blood sugar determined by HbA1c > 6.5% (and < 10.0%) at both the screening and randomization visits
- 7) No changes in diabetes medication in the previous month
- 8) DSM-5 criteria for Insomnia Disorder
- 9) Score on the Insomnia Severity Index (ISI) measure > 10, indicating at least a moderate level of insomnia symptoms
- 10) Report a total sleep time  $\leq$  6.5 hours and a combined sleep onset latency (SOL) and wake after sleep onset (WASO) > 45 minutes on 7 or more of the 14 nightly sleep logs during both the initial 2-week screening period and the two-week screening run-in period. Combined SOL and WASO does not decrease by more than 50% on the 2-week sleep diary obtained between the screening visit and the randomization visit.

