### **Study Design and projected enrollment:**

This is a parallel, two-arm, double-blind, randomized placebo-controlled 3-month trial using the sequential parallel comparison design (SPCD), investigating the effects of suvorexant 10–20 mg on subjective total sleep time in patients with suboptimally controlled Type 2 diabetes. The SPCD consists of two stages, with data being pooled from both stages. The first phase involves an unbalanced randomization between placebo and active treatment with more patients randomized to placebo. In the second phase, non-responders treated with placebo are re-randomized to either active treatment or placebo. The first stage is a standard parallel comparison design. However, this first stage generates a cohort of placebo non-responders who then enter the second stage where placebo responses will be lower. This design enriches the primary analysis population, reducing the impact of placebo response rates, and allowing trials to be conducted with reduced study sample size without corresponding decreases in statistical power.

All study procedures will be conducted at Massachusetts General Hospital. We expect to consent and evaluate for eligibility up to 120 Type 2 diabetics in order to achieve our projected randomized sample size of 72 patients with Type 2 diabetes. Subjects will be randomized in a 1:2 ratio to suvorexant 10–20 mg or equivalent placebo for six weeks followed by re-randomization of placebo non-responders to either suvorexant or placebo in a 1:1 design; this will allow 62 Type 2 diabetics to complete the trial at 3 months, after allowing for post-randomization drop-outs.

Eligible patients will be randomized to 6 weeks of suvorexant or placebo after an initial 2-week screening period and a two-week screening run-in period to ensure the stability of sleep disturbance. Participants will complete 4 study visits (consent/screening visit, randomization visit, a 6-week visit, and a 3-months-on-treatment visit). In addition, an initial telephone-based screening assessment and 2 interim phone visits (at 1 week and 7 weeks on treatment) will occur. Suvorexant will be started at 10 mg nightly for the first 7 days. If the 10-mg dose is well tolerated but not effective after one week of treatment, as determined by the one-week phone visits (at 1 week and 7 weeks of treatment for those originally randomized to suvorexant and placebo, respectively), the dose can be increased to 20 mg.

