### **SCREENING VISIT:**

Written informed consent will be obtained by the study doctor at the Screening Visit for the remaining screening procedures and all treatment-related procedures (via the IRB-approved Informed Consent Form via the REDCap e-consent framework). Risks and benefits associated with use of suvorexant will be described. At that time, further eligibility will be assessed with a clinical interview conducted by a sleep medicine-trained psychiatrist to diagnose chronic insomnia disorder and to ensure that contraindicated sleep, medical and psychiatric problems and medications are excluded. At in-person visits, vital signs will be obtained, urine screens collected for pregnancy and disallowed substances, and blood will be drawn for HbA1c and C-Reactive Protein. When the Screening Visit is virtual, the subject will have the pregnancy, drug, HbA1c, and C-Reactive Protein tests performed at an affiliated site or a satellite clinic; the study physician will order these tests. The drug screen will only be performed at the Screening Visit.

Screening Run-In: They will receive daily email links to an online sleep diary to complete on 14 consecutive days during the screening run-in period.

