**Table of Procedures:**

Visit	Screening Period			Treatment Period			
	Pre-V1	V1/ Screening	V2/ Randomizat ion	Phone contact 1	V3/ Placebo non- responder re- randomization	Phone contact 2	V4/ Treatment End
Study Week	-4	-2	0	1	6	7	12
Visit Location	Phone	Office/ Phone	Office/ Phone	Phone	Office/Phone	Phone	Office/ Phone
General/ Screening Assessment	Sleep/medical/mental health phone screening and verbal consent	x					
	Written Informed Consent		x				
	Eligibility Criteria	x	x				
	Medical History & Physical Exam		x a				
	Urine hCG	x			x		
	Drug Panel Urinalysis	x					
	Concomitant Medication	x	x	x	x	x	x
	ISI	x	x		x		x
	PGI-I				x		x
	BDI		x		x		x
Vitals	DQOL		x		x		x
	Diabetes Distress Scale		x		x		x
Lab Tests	Height/Weight/Heart Rate/Blood Pressure		x a	x a		x a	x a
	HbA1c	x	x b		x		x
Sleep Assessment	CRP	x	x b		x		x
	Sleep Diaries (administer/review)	x c	x c		x d		x d
Medication Dispensing *by mail	PSQI		x		x		x
			x	x*	x	x*	
Safety Assessment/ Adverse Event Reporting				x	x	x	x
					x		x
Medication Adherence							

Conditional study procedure: a = only performed at in-person visit  
b = only performed if four weeks have passed between Screening and Randomization Visits  
Study procedures completed between study visits: c = daily for 2 wks following visit, d = daily for 2 wks prior to visit

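### Minor participant-safety point: no pregnancy test is scheduled at Randomization, so the Screening result may be about 2 weeks old at first dose, or over 4 weeks old with no stated maximum

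*Combined protocol and SAP*

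**What the plan says.** - **Eligibility.** Section III admits men and women aged 25 to 75. Exclusion 3b bars pregnant or breastfeeding participants.
- **Screening Visit (Section V).** The text says "At in-person visits, vital signs will be obtained, urine screens collected for pregnancy and disallowed substances". For remote participants it says "When the Screening Visit is virtual, the subject will have the pregnancy, drug, HbA1c, and C-Reactive Protein tests performed" at an outside site. This is the only place where the prose describes a pregnancy test.
- **Randomization Visit (Section V).** Diaries and "laboratory results will be reviewed for definitive eligibility before the participant is randomized to treatment". The text also says "HbA1c and C-Reactive Protein tests will only be performed at the Randomization Visit if more than 4 weeks have elapsed" since Screening. Footnote b of the Table of Procedures gives the same condition ("only performed if four weeks have passed between Screening and Randomization Visits") and is attached to the HbA1c and CRP rows, not to the urine hCG row.
- **Timing.** Randomization follows "after an initial 2-week screening period and a two-week screening run-in period" (Section IV, Study Design). The table puts Screening at week -2, Randomization at week 0 and the re-randomization visit at week 6. No upper limit is given for the interval from Screening to Randomization.

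**The concern.** The plan excludes pregnant women but appears to schedule no pregnancy test at the visit where dosing begins. It relies on the Screening result and foresees that Randomization may come more than 4 weeks later. It does not say how old that result may be. A woman who conceives after the Screening test could start study drug, and the next scheduled test is at week 6. What is at stake is the safety of a small number of participants, not the analysis.

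**Working it through.** **1. Where the two hCG marks fall.** The table was damaged in extraction, so the columns have to be inferred.

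- The drug-panel row has one mark, in the same first position as the first hCG mark. The Screening Visit text confines the drug screen to Screening, so that position is V1.
- In the HbA1c and CRP rows the second mark carries footnote b, which the prose ties to Randomization. The second position is V2.
- The remaining marks in those rows, in positions 4 and 6, then fall at V3 (week 6) and V4. The PGI-I row has its marks in the same two positions.
- The hCG marks stand in positions 1 and 4, that is V1 and V3. Position 2 (V2) is blank.

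A cross-check uses the seven printed columns: Pre-V1, V1, V2, Phone 1, V3, Phone 2, V4.

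| Gap between the two marks | Possible placements | Placements that avoid a phone contact |
|---|---|---|
| 3 columns (as printed) | 4 | V1/V3 only |
| 4 columns (if an inner blank was lost) | 3 | V2/V4 only, which has no Screening test and so conflicts with the prose |

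Other rows (consent, physical exam, vitals, diaries) are shifted in different ways. The diary footnotes ("c = daily for 2 wks following visit, d = daily for 2 wks prior to visit") show that the diary row has lost an inner column. The placement is therefore an inference, though a well-supported one.

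**2. Age of the hCG result.**

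| | On schedule | Randomization delayed |
|---|---|---|
| Screening test to first dose | 0 - (-2) = 2 weeks | more than 4 weeks, no maximum |
| Screening test to next test | 6 - (-2) = 8 weeks | more than 4 + 6 = 10 weeks |

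**3. Why HbA1c and CRP are repeated.** HbA1c must qualify "at both the screening and randomization visits" (inclusion criterion 6), and both tests are trial outcomes. Those reasons explain the repeat without any reference to safety.

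**4. Size.** From the documents, 72 are randomized 1:2, so 72/3 = 24 receive suvorexant in the first period. The other inputs are assumptions that are not in the documents:

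- share of the 72 who are women able to conceive: 10 to 30%
- share of these randomized late, with a gap of 4 weeks: 10 to 50%
- conception risk per month (4.345 weeks): 0.1 to 1%

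Formulas: late tests = 72 × share × late fraction. Conceptions in the gap = late tests × [1 - (1 - monthly risk)^(4/4.345)]. One third of these fall on suvorexant.

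- Low: 72 × 0.10 × 0.10 = 0.72 tests; 0.72 × 0.00092 = 0.0007 conceptions; /3 = 0.0002 on suvorexant.
- High: 72 × 0.30 × 0.50 = 10.8 tests; 10.8 × 0.00921 = 0.10 conceptions; /3 = 0.03 on suvorexant.

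If every Randomization visit included a test, the number of tests would be 72 × 0.10 = 7.2 to 72 × 0.30 = 21.6. The participants randomized on time, with a 2-week gap, would add:

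- Low: 6.48 × 0.00046 = 0.003 conceptions.
- High: 10.8 × 0.00462 = 0.05 conceptions.

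The whole-trial total would then be about 0.004 to 0.15. These are upper bounds on what a test could find, because a urine test misses very recent conceptions. A delay longer than 4 weeks beyond Screening would raise the figures for late participants.

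**The case against.** The strongest reply is that the prose is more open than the table suggests. The Screening text speaks of in-person visits in the plural. It then limits the drug screen, but not the pregnancy test, to Screening. The Randomization text restricts only HbA1c and CRP. One could read this as allowing a pregnancy test at an in-person Randomization visit. But the week 6 test already explains both the plural and the need to limit the drug screen. The sentence also stands under the Screening heading, and nowhere do the documents state a test at Randomization. If one was intended, a clarifying line is still needed.

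Second, the column placement is a reconstruction of a damaged table. That is true and limits confidence. The damage is not itself an error in the plan.

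Third, there are partial safeguards. Pregnancy is an exclusion whatever the test date, eligibility is reviewed before randomization, the planned interval is two weeks, and hCG is tested again at the visit where placebo non-responders are re-randomized. All of this stands, and it is why the point is minor.

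A reader might also infer that hCG was left out of a safety rule, or that the protocol contradicts itself. The documents support neither. The 4-week repeat serves eligibility and outcome measurement, and no statement conflicts with another. Nor can one conclude that contraception goes unaddressed: consent pages were removed and cannot be assessed.

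**Conclusion.** The point holds as a minor participant-safety improvement, with medium confidence because the table columns are inferred. On the likeliest reading, the first dose rests on a pregnancy result about 2 weeks old on schedule, and more than 4 weeks old without a stated maximum when Randomization is late. How often Randomization is late is not given. The expected number of affected pregnancies is well below one under every combination of the assumptions above: at most 0.10 among late participants in the whole trial, of which 0.03 on suvorexant. It would be wrong to read this as a threat to the trial's conclusions, because power, bias, type I error and the estimate are untouched. The case for change is that a stated exclusion should be checked close to first dosing when that costs almost nothing.

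**What to change.** For women able to conceive:

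1. Add urine hCG at V2 when that visit is in person.
2. Add it in all cases, including remote visits, when more than 4 weeks have passed since Screening, by extending footnote b and the repeat rule under the Randomization Visit to hCG.
3. Require a negative result before drug is dispensed or mailed.
4. State in the visit text which visits include the pregnancy test.

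The cost is a few words by amendment and, on the assumptions above, somewhere between the late-only count (0.7 to 11 tests) and the count for every V2 (7 to 22 tests). The in-person test adds no travel. In the late case a laboratory stop for HbA1c and CRP is already required, and the HbA1c result, itself an eligibility criterion, should already hold up dispensing; otherwise some remote participants wait a short time for the mailing. Two gaps remain: a remote participant randomized on time still relies on a result about 2 weeks old, and conceptions after V2 are not detected until week 6.

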**Randomization:**

Randomization will be used to avoid bias in the assignment of subjects to treatment, to increase the likelihood that known and unknown subject attributes (e.g., demographics and baseline characteristics) are evenly balanced across treatment groups, and to enhance the validity of statistical comparisons across treatment groups. Blinded treatment will be used to reduce potential bias during data collection and evaluation of clinical endpoints. An unblinded research coordinator will be responsible for all re-randomization determinations and communicating with the pharmacy in that regard.

At the Screening Visit, subjects will be assigned a 3-digit subject number, in ascending sequential order beginning with 001. The subject number will be retained by the subject for the duration of the study. The MGH Clinical Trials Pharmacy and unblinded research coordinator will provide and maintain randomization and blinding. Subjects will be randomized to receive either suvorexant or placebo in a 1:2 ratio, and placebo non-responders will be re-randomized to suvorexant or placebo in a 1:1 ratio at the 6-week visit. The re-randomization will be balanced by using permuted blocks of 4. Subject and investigator will be blinded to treatment assignment. Subjects will be randomized sequentially as they qualify for the study.

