**Blinding:**

The randomization code will be maintained by the MGH Clinical Trials Pharmacy and will not be revealed to study subjects, investigators or blinded clinical staff until all subjects have completed and the database has been finalized.

Under normal circumstances, the blind should not be broken. The blind should be broken only if specific treatment would be dictated by knowing the treatment status of the subject. Individual code breaks by the investigator will normally result in withdrawal of the subject from the trial. The date, time and reason for the unblinding must be documented in the study files.

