### **VIII. STATISTICAL ANALYSIS**

Analysis of all study data will be conducted by [name] and [name], a statistician at Massachusetts General Hospital. All study personnel and participants will remain blinded to treatment assignment, including staff entering study data. Only the unblinded research coordinator, who will assess treatment response at 6-weeks, and the hospital Research Pharmacist who generates the randomization code will be unblinded to treatment assignment. The final database will not be unblinded until a medical and scientific review, protocol violators have been identified, and all study data are complete.

The sequential parallel comparison design was developed at Massachusetts General Hospital and has been used extensively in clinical trials funded by both industry and NIH. Experts at MGH in SPCD will be consultants in the statistical analyses of our data.

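### Concealment of the week-6 re-randomization is not secured by procedure: the coordinator who classifies placebo non-responders also shares in maintaining the randomization, with no lock before assignment

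*Combined protocol and SAP*

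**What the plan says.** **Who classifies.** The section on the randomization visit and treatment period says: "The placebo non-responders will be determined by the unblinded research coordinator". The basis is two weeks of diaries before the 6-week visit. The Statistical Analysis section confirms the role: "Only the unblinded research coordinator, who will assess treatment response at 6-weeks".

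**Who holds the randomization.** The Randomization section gives the coordinator two functions: "An unblinded research coordinator will be responsible for all re-randomization determinations and communicating with the pharmacy in that regard", and "The MGH Clinical Trials Pharmacy and unblinded research coordinator will provide and maintain randomization and blinding". The Blinding section says: "The randomization code will be maintained by the MGH Clinical Trials Pharmacy and will not be revealed to study subjects, investigators or blinded clinical staff". The Statistical Analysis section refers to "the hospital Research Pharmacist who generates the randomization code will be unblinded to treatment assignment".

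**How stage 2 is allocated.** Allocation is 1:1, and "The re-randomization will be balanced by using permuted blocks of 4". The supplied text gives no response variable or cut-off. The study flowchart is not shown and may contain one.

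**Dispensing.** The Dispensing Schedule table has a separate column for placebo non-responders that restarts at 10 mg in week 6, while the other two columns continue at either strength. The Packaging section has bottles labelled by strength. The Randomization section says: "Subject and investigator will be blinded to treatment assignment".

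**The concern.** The stage 2 comparison is one of the two weighted components of the primary analysis. It is unbiased only if the decision to admit a patient to stage 2 cannot depend on the arm that patient would receive. If the person who judges response also knows or can predict the next assignment, a borderline patient can be admitted when one arm is next and held back when the other is next. Randomization does not protect against that.

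Someone must know the stage 1 arm, because only placebo patients are re-randomized. That is inherent in the design. Giving the same person a share in running the stage 2 randomization is not.

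The dispensing question is separate. It concerns the stage 1 blind, where recognition of stage 1 placebo could alter expectation, and so the placebo response, in the second six weeks.

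**Working it through.** **1. Reading the sections together.** The plan states no figure to reproduce here.

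- *Custody.* The Randomization section names the pharmacy and the coordinator. The Blinding section names the pharmacy alone. The Statistical Analysis section has the pharmacist generate the code. Generating a code does not settle who may see it.
- *Access.* The Blinding section withholds the code from subjects, investigators and blinded clinical staff. The unblinded coordinator is not in that list. Omission is not proof of access, but no other sentence supplies a bar.
- *Order of events.* No section requires the classification to be recorded before the assignment is released. The only safeguard of that kind concerns unblinding of the final database.

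**2. Predictability of blocks of 4 at 1:1.** Suppose a person knows the earlier assignments and the block size. The chances of guessing positions 1 to 4 correctly are 1/2, 2/3, 2/3 and 1. They sum to 17/6 = 2.83 per block, or 17/24 = 71%. Assignments known with certainty number 1/3 + 1 = 1.33 per block, or one third.

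**3. Size of the bias (illustration).**

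From the protocol: 72 randomized 1:2, so 24 suvorexant and 48 placebo; two-sided 5% test; adjustment for baseline total sleep time (TST), with baseline taken from the run-in diaries.

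Assumed: no drug effect; 60% non-response, so 0.6 × 48 = 28.8 re-randomized; stage 1 weight 0.5 (none is stated); TST at run-in, week 6 and week 12 normal with SD 1; correlations all 0.5, all 0.7, or 0.6/0.7/0.5 (run-in with week 6, week 6 with week 12, run-in with week 12); weighted z test at 1.96.

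A borderline case lies within ±0.25 SD of the cut-off on stage 1 change. With the cut-off at z = 0.253, that share is Φ(0.503) − Φ(0.003) = 0.19, or about 9.2 of 48. Full steering admits all of them when drug is next and none when placebo is next. It reclassifies half: 9.2/2 = 4.6.

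Results with each stage adjusted for run-in TST only (120,000 trials per setting, Monte Carlo SE about 0.07 points; ranges are over the correlations):

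| Scenario | Reclassified per trial | Stage 2 shift (SD of TST) | Two-sided type I error |
|---|---|---|---|
| No steering | 0 | none | 5.5–5.6% |
| Block guessing | 2.7 | 0.034–0.059 | 5.7–6.0% |
| List known, half steered | 2.3 | 0.042–0.071 | 5.7–5.9% |
| List known, all steered | 4.6 | 0.083–0.146 | 6.1–7.3% |

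Smaller repeat runs put the last row as high as 7.5%. The unsteered rate exceeds 5% because 1.96 is used in small samples, so the fair comparison is with the first row. At weight 0.5, the pooled shift in the last row is half the stage 2 shift, 0.041 to 0.073 SD.

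**4. Sensitivity of the last row.**

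- *Weight.* Stage 1 weight 0.7 gives 5.5–6.0% (unsteered 5.2–5.3%). Weight 0.3 gives 6.7–8.5% (unsteered 5.9–6.0%).
- *Band.* ±0.5 SD (17.9 of 48, 37%) gives 7.7–12.7% at weight 0.5.
- *Stage 2 covariate.* This decides both sign and size. Week-6 TST alone turns the shift negative, about −0.03 to −0.09 SD, against the drug. Adjusting for both run-in and week-6 TST brings it to about zero (below 0.007 SD in absolute value), with type I error 5.5–5.7%, and 5.7–5.8% for the ±0.5 SD band. The reason is that steering on recorded change selects only on those two values.

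**5. Dispensing.** In the table, only placebo non-responders restart at 10 mg at week 6. A patient who moves from a bottle labelled 20 mg to one labelled 10 mg is thereby identifiable as stage 1 placebo to anyone who knows the protocol. Both re-randomized arms restart alike, so the move says nothing about the stage 2 arm. The Study Design section, read literally, also ties the week-1 dose decision to those originally on suvorexant and the week-7 decision to those originally on placebo. The table nevertheless lists both strengths for placebo in weeks 2–5. The documents do not say how many patients will be on 20 mg, so the number affected cannot be derived.

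**The case against.** The sections can be read as one workflow: the coordinator classifies, tells the pharmacy, and the pharmacy assigns. On that reading the shared-maintenance sentence is loose operational wording, and a lock-and-release step may sit in pharmacy procedures. The diaries are electronic and patient-reported, and the missing flowchart may hold a numeric rule. Steering would then mean misclassifying against recorded data.

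Most of this is fair, and it limits what can be claimed. A reader might infer that the coordinator holds the stage 2 list, that concealment has failed, or that the primary test is materially inflated. The documents support none of these. Access to the list is nowhere stated, and the simulated inflation needs that access together with consistent one-way steering. A simpler stage 2 simulation, unadjusted and with milder steering, found shifts of at most about 0.05 SD with the list known and type I error near 5%.

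What stands is that the benign workflow is an interpretation. The current text assigns maintenance jointly and states no bar and no lock, and those gaps do not depend on the flowchart. Covariate adjustment is no substitute for concealment: it removes only steering on recorded sleep times, and the analytic overview points to baseline adjustment alone.

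On dispensing, the week-7 call is scheduled for everyone, and the 14-day supply after week 6 is not limited to non-responders. Whether patients know what a step down means cannot be checked, because the consent pages were removed. Blinded staff do have the protocol. A reader might also infer that the label change biases the stage 2 comparison. It does not reveal the stage 2 arm, and no difference between arms is shown.

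**Conclusion.** The concern holds as a gap in procedure. One role classifies non-responders and is also given a share in the randomization, the sections differ on custody, and no lock is required before assignment. Concealment of stage 2 is not assured, but it is not shown to be broken.

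The expected bias is small. Block guessing is essentially harmless. About 6 to 7.5%, against 5.5–5.6% unsteered, is reached only with list access, every borderline case steered one way, a ±0.25 SD band, weight 0.5 and run-in adjustment alone. The non-response rate, weight, band and correlations are assumptions, and another stage 2 covariate reverses or removes the shift. The amendment is worth making because it costs little, not because a large error is likely.

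The dispensing conflict is real, separate and lesser. It bears on the stage 1 blind only, and its extent is unknown.

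**What to change.** **Stage 2 concealment.** Amend the Randomization section so that the pharmacy alone holds the stage 2 list and the earlier stage 2 assignments, in line with the Blinding and Statistical Analysis sections. Classify every stage 1 placebo patient by one prespecified diary rule, with variable and cut-off chosen by the sponsor, computed in REDCap. Record and lock the result before the pharmacy releases an assignment. Varied block sizes are optional and add little once the pharmacy alone holds the list.

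*Cost:* a wording change, one calculated and locked field, and one release step. Discretion in borderline cases is lost. Sample size, power and alpha are unchanged.

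**Stage 1 blind.** Reconcile the Study Design, Dispensing Schedule and Packaging text with the Randomization and Blinding sections, so that neither week-6 dispensing nor the week-7 review discloses the stage 1 arm. Relabelling alone is not enough, because the week-7 review is also tied to the original arm. No dose or titration rule is proposed here.

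*Cost:* protocol wording, possibly new week-6 labels, and some pharmacy work, since strength must stay available to the pharmacy for the taper and the CYP3A provisions.
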